### 1.3.3 Sample Size and Statistical Power Considerations

A group size of 30 participants per dose was deemed sufficient to evaluate the potential safety and tolerability of IKT-148009. A sample size of 30 per group would provide > 80% power to detect a 5 point difference in the change from baseline UPDRS II + III between groups with a standard deviation of 6 points, a drop-out rate of 10%, and alpha = 0.05. Secondary measures will use appropriate descriptive statistics to assess study outcomes.

## 2 STATISTICAL CONSIDERATIONS

### 2.1 GENERAL CONSIDERATIONS

SAS® 9.4 or higher will be used to perform all analyses.

All descriptive statistics for continuous variables will be reported using the number of non-missing participants (n), mean, standard deviation (SD), median, minimum and maximum. Categorical variables will be summarized as number and percentage of participants.

The default significance level will be 0.05. p-values will be rounded to three decimal places. If a p-value is less than 0.001 it will be reported as “<0.001”. A p-value greater than 0.999 will be reported as “>0.999”.

Minimum and maximum values will be rounded to the precision of the original value. Means and medians will be rounded to one decimal place greater than the precision of the original value. SD and Confidence Intervals (CI) will be rounded to two decimal places greater than the precision of the original value. Percentages for summarizing categorical data will be rounded to one decimal place.

The number of below the limit of quantitation (BLQ) values, i.e., the n below lower limit of quantification (LLOQ), will be reported for each time point. All study data will be included in study data listings. In general, all data will be listed by time point within

participants. All summary tables will present descriptive statistics for the parameters being analyzed.

## 2.2 DEFINITIONS OF ANALYSIS SETS

The number of participants who signed the Informed Consent Form (ICF), the number and the percentage of participants included in each analysis set, and the number and the percentage of participants excluded from each analysis set will be presented by dose group and overall. Reasons for exclusion from each analysis set will also be summarized. Reasons for exclusion from the mITT analysis of efficacy include:

- Did not have a valid baseline MDS-UPDRS score
- Did not receive at least one dose of study drug
- Did not have at least one valid post-baseline evaluation of the MDS-UPDRS score
- Randomized prior to Protocol version 6.1

Reasons for exclusion from the Safety analysis set include:

- Did not receive at least one dose of study drug

There are four analysis sets:

Analysis Set	Description
Modified Intent to Treat (mITT)	The mITT population will include all randomized participants who have a valid baseline MDS-UPDRS, received at least one dose of study drug, and have at least one post-baseline evaluation of the MDS-UPDRS assessment. Participants randomized prior to Protocol version 6.1 will be excluded. Participants will be analyzed according to their assigned intervention. This set will be used to analyze efficacy endpoints.
Safety	The Safety analysis set will include all participants received at least one dose of study drug. in the Safety analysis set will be analyzed according to the intervention that they actually received.
Per-protocol Set (PP)	Includes all participants in the mITT analysis set who complete the study without a major protocol deviation deemed as impacting the secondary efficacy endpoints.
Full Analysis Set (FAS)	The FAS will include all randomized participants who have a valid baseline MDS-UPDRS, received at least one dose of study drug, and have at least one post-baseline evaluation of the MDS-UPDRS assessment. Participants randomized prior to Protocol version 6.1 will be included. Participants will be analyzed according to their assigned intervention. This set will be used for sensitivity analysis.

Protocol deviations will be identified programmatically as well as based on protocol deviations collected by the study monitors. After the last participant exits the trial and prior to database lock, protocol deviations will be reviewed to determine which participants fall into these categories.

## 2.3 DEFINITIONS AND CONVENTIONS FOR DATA HANDLING

### 2.3.1 Baseline Definition

Unless otherwise noted, the last value observed prior to the first administration of study intervention on Day 1 will be the baseline value. If there is no value prior to the study intervention, then the baseline value will not be imputed, and will be set to missing.

### 2.3.2 Study Day

Study Day will be calculated from the reference start date and will be used to show start/stop day of assessments and events.

Reference start date (Day 1) is defined as the day of first administration of study intervention.

- Study Day = (date of event – reference start date +1) if the event date is on or later than reference start date
- Study Day = (date of event – reference start date) if the event date is earlier than reference start date

There is no Study Day 0. In the situation where the event date is partial or missing, Study Day, and any corresponding durations will appear partial or missing in the listings.

### 2.3.3 End of Study

A participant is considered to have completed the study if he/she completes all visits in accordance with the Protocol SoA (Section 1.3).

The end of study is defined as the date of the last visit of the last participant in the study or last scheduled procedure, shown in the SoA for the last participant in the study globally.

### 2.3.4 Analysis Visit Windows

The analysis time point assigned for the post-baseline visits will be assigned based on the analysis windows described in [Table 2-1](#):

**Table 2-1 Analysis visit windows for measurements**

Adjusted Defined Windows Visit	Scheduled Study Day	Maximum Windows
Baseline (Day 1)	1	Study Day =1
Week 4	29	$2 \leq \text{Study Day} \leq 43$
Week 8	57	$44 \leq \text{Study Day} \leq 71$

Adjusted Defined Windows Visit	Scheduled Study Day	Maximum Windows
Week 12	85	$72 \leq \text{Study Day} \leq 91$
Safety follow-up	99	$92 \leq \text{Study Day}$

Applying the above visit window rules will be done after identifying treatment visits by CRF visit labels.

### 2.3.5 Missing Data Handling Rules

Unless otherwise noted, missing data will not be imputed but will be analyzed as missing.

Any participant with a missing Week 12 visit is defined as a non-completer.

Some individual scales or subscales have their own guidelines for missing items, which will be described in [Section 3.2](#) along with the scale. Unless otherwise specified, if  $\leq 20\%$  of the total number of items are missing, then the mean score of the non-missing items for that scale or subscale will be calculated, rounded up to the nearest integer, and imputed to the missing item(s). Otherwise, the assessment score will be set to missing.

Handling of partial or missing dates for adverse events (AEs), concomitant medication start or end dates, and death dates are described in [Appendix 8.1](#). Missing AE severity or relationship will be reported as missing.

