### 3.2.2 Parkinson's Disease Questionnaire (PDQ-39)

The PDQ-39 is a self-administered questionnaire that assesses how often people affected by PD experience difficulties across 8 dimensions of daily living, including mobility (10 items), activities of daily living (6 items), emotional well-being (6 items), stigma (4 items), social support (3 items), cognition (4 items), communication (3 items), and bodily discomfort (3 items).

Each item is scored as one of 5 ordered response categories. Each dimension score is summed then divided by the number of items and multiplied by 100 to get a percentage score ranging from 0 to 100, with lower scores indicating better health and higher scores more severe symptoms. The PDQ-39 is scored by taking the sum of the 8 scale scores, divided by the number of dimensions (8), which yields a score between 0 and 100 ([Hagell 2009](#)).

CFB will be calculated for Visits 2 (Week 4), 3 (Week 8), 4 (Week 12), and 5 (Safety follow-up). A negative CFB reflects improvement.

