### 3.2.5 MDS-UPDRS Part II

This endpoint uses the results from MDS-UPDRS Part II (Motor Aspects of Experiences of Daily Living), which has 13 items. Item scores are totaled with a range from 0-52.

CFB will be calculated for Visits 2 (Week 4), 3 (Week 8), 4 (Week 12), and 5 (Safety follow-up). A negative CFB reflects improvement.

A total Part II score can be calculated if up to 2 items are missing, assuming that items are missing at random across participants ([Goetz et al, 2015](#)). The total score is calculated as the  $[(\text{sum of non-missing scores}) \times (\text{total number items})] / (\text{number of non-missing scores})$ .

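### The default rule for missing questionnaire items is written as a ceiling, so it adds about half a raw point per imputed item to PDQ-39, NMSS and most PAC-QoL items

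*SAP*

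**What the plan says.** SAP 2.3.5 sets a default for incomplete questionnaires. If no more than 20% of items are missing, "the mean score of the non-missing items for that scale or subscale will be calculated, rounded up to the nearest integer, and imputed" in place of each missing item; above that limit the score is missing. The default gives way where a scale has its own rule: "Some individual scales or subscales have their own guidelines for missing items, which will be described in" SAP Section 3.2.

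Section 3.2 gives such rules for these scales:
- **MDS-UPDRS Parts I, II and III** (3.2.5 to 3.2.7): prorated without rounding. For Part II, "A total Part II score can be calculated if up to 2 items are missing".
- **ESS** (3.2.10): missing if any item is missing.
- **PAGI-SYM and PAGI-QoL** (3.2.12, 3.2.14): subscale means, with a 50% limit.

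PGI-S, CGI-S and SE-ADL are single items, and CSBM is a diary count. That leaves PDQ-39 (3.2.2), NMSS (3.2.8) and PAC-QoL (3.2.13) without a rule, so the default governs them.

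On PDQ-39 the SAP reads direction as "lower scores indicating better health and higher scores more severe symptoms". On all three scales a negative change from baseline is improvement.

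**The concern.** Replacing a missing item with the person's own mean is a neutral choice when items are missing at random. Rounding that mean up is not: 0.25 becomes 1, and a mean just above 1 becomes 2. The error has one sign, and no integer is needed, because these scores are sums or averages. The same SAP handles missing MDS-UPDRS items by unrounded proration, so one plan treats the same problem in two ways.

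A missing post-baseline item moves change from baseline toward worsening, and a missing baseline item moves it toward improvement. PDQ-39 is the most exposed of the three endpoints because SAP 2.4 places it second in the testing order.

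**Working it through.** The plan states no figure on this point to reproduce. The check is arithmetic, plus a simulation under assumed item distributions.

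**1. Shift per imputed item.** Let m be the mean of the observed items. The rule imputes ceil(m), so the shift against the unrounded mean is ceil(m) - m. It is at least 0, equals 0 when m is an integer (for example, all observed items are 0), and is at most 1 - 1/(number of observed items). For PDQ-39 with one item missing the maximum is 1 - 1/38 = 0.97.

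**2. Unrounded imputation equals proration.** With k items, n observed and observed sum S: S + (k - n) x S/n = S x k/n. This is the MDS-UPDRS formula.

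**3. How many items can be imputed.**
- If the 20% limit applies to the whole scale: 7 of 39 (PDQ-39), 6 of 30 (NMSS), 5 of 28 (PAC-QoL).
- If it applies per subscale, the subscale needs at least 5 items. That leaves the 10-, 6- and 6-item dimensions of PDQ-39, the 6-item mood/cognition domain of NMSS (one item), and the 8-, 5- and 11-item domains of PAC-QoL.

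All three scales are affected on either reading.

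**4. PDQ-39 example.** SAP 3.2.2 says "Each item is scored as one of 5 ordered response categories" without giving codes, and "Each dimension score is summed then divided by the number of items and multiplied by 100" without dividing by the maximum item score. I assume 0-4 coding and scale to the 0-100 range the section states. Mobility has 10 items; suppose 2 are missing and the 8 observed sum to 2 (m = 0.25, assumed).
- Round-up: (2 + 2 x 1)/40 x 100 = 10.00
- Unrounded: (2 + 2 x 0.25)/40 x 100 = 6.25
- Difference: 3.75 on the dimension, and 3.75/8 = 0.47 on the index.

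One whole item unit is worth 100/(4 x 10)/8 = 0.31 index points in the 10-item dimension and 100/(4 x 3)/8 = 1.04 in a 3-item dimension.

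**5. PAC-QoL examples.** Psychosocial domain, 7 of 8 items observed with sum 8: m = 1.14 is imputed as 2, so the domain is 10/8 = 1.25 instead of 1.14. Items 25 to 28 are reverse-scored, and SAP 3.2.13 does not say whether reversal comes before imputation. If imputation comes first, a raw mean of 2.25 becomes 3 and then 4 - 3 = 1, against 4 - 2.25 = 1.75 unrounded. For those four items the score then moves down.

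**6. Average shift.** Simulation, 20,000 forms per setting, items missing at random. The 0-4 items had average levels from low to mid-scale; NMSS items had 15%, 30% or 50% of symptoms present. All of these distributions are assumptions.

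| Setting | Missing | Round-up bias in raw sum |
|---|---|---|
| 39 items, 0-4 | 1 | +0.49 to +0.59 |
| 39 items, 0-4 | 7 | +3.3 to +4.1 |
| 10-item dimension, 0-4 | 2 | +0.88 to +1.05 |
| 28 items, 0-4 | 1 | +0.47 to +0.60 |
| 28 items, 0-4 | 5 | +2.3 to +3.0 |
| NMSS, whole scale | 1 | +0.47 to +0.51 |
| NMSS, whole scale | 6 | +2.8 to +3.0 |
| NMSS, 6-item domain | 1 | +0.25 to +0.38 |

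The unrounded mean gave a bias of at most 0.06 in absolute value throughout. Ordinary rounding gave -0.52 to +0.19. The 28-item rows ignore item reversal.

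**7. Trial-level illustration (assumed).** Suppose the arms differ by d in the proportion of Week 12 forms with one imputed item. For PDQ-39 I use the ceiling of 1.04 index points per item, and for NMSS the average of 0.5 points.

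| d | PDQ-39 index, at most (0-100) | NMSS, average (0-360) |
|---|---|---|
| 0 | 0 | 0 |
| 5 points | 1.04 x 0.05 = 0.05 | 0.5 x 0.05 = 0.025 |
| 10 points | 1.04 x 0.10 = 0.10 | 0.5 x 0.10 = 0.05 |
| 20 points | 1.04 x 0.20 = 0.21 | 0.5 x 0.20 = 0.10 |

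**The case against.** The best defence is about consequence. The trial is randomized and double-blind, so equal item missingness with similar item means shifts all arms alike and largely cancels. The primary objective is safety, and the leading efficacy endpoint, MDS-UPDRS Parts II + III, is prorated and untouched. PDQ-39 is tested formally only if that endpoint is significant at the high dose; otherwise its test is nominal under SAP 2.4. All of this stands, and it is why the point is minor.

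The phrase may also be loose wording for ordinary rounding, which would leave only a small bias of either sign. That is possible, but a programmer following the text would code a ceiling, so the wording needs correcting either way.

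Several stronger readings are tempting, and the documents do not support them:
- **An incomplete Week 12 form is scored as worsening.** It is only moved in that direction, by less than one raw unit per imputed item. A real improvement can still show as one.
- **NMSS totals are inflated by 3 points or more.** That needs several imputed items, which is possible only if the 20% limit applies to the whole scale. Per domain, at most one NMSS item can be imputed.
- **These participants have low item scores, so relative inflation is large.** Neither document reports baseline scores.
- **PAC-QoL always moves up.** Items 25 to 28 can move down, as shown.

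**Conclusion.** The rule is wrong as written: on a literal reading it introduces an avoidable error, upward apart from the PAC-QoL reversal case, in three endpoints of the testing hierarchy. The size is about 0.5 raw points per imputed item on average when the mean is taken over the whole scale, and about 0.25 to 0.53 in the two subscales simulated. These averages rest on assumed item distributions, and the PDQ-39 point values rest on 0-4 coding.

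A reader might infer that the treatment comparisons, or the PDQ-39 step in the testing sequence, are biased. The documents do not show that. It would require item missingness, or item means on incomplete forms, to differ by arm, and no item-missingness rate is given. In the illustration, a 20-point imbalance in forms with one imputed item moves the PDQ-39 index by about 0.2 of 100 points at most. The trial-level effect is probably small. Severity: minor.

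**What to change.** In SAP 2.3.5, delete the instruction to round up and impute the unrounded mean of the answered items. This matches the MDS-UPDRS proration; the 20% limit can stay. In the same edit:
- State whether the 20% limit and the mean apply per scale or per subscale.
- State that PAC-QoL items 25 to 28 are reversed before imputation.

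The cost is a short SAP edit and about one line of code, with no new data. If the SAP can no longer be amended, SAP Section 1 already provides for recording deviations in the clinical study report. The report should then note the change and give the number of affected forms by arm and visit.

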### 2.3.6 Other Data Points Definition

A screen failure is defined as a participant who consents to participate in the clinical study but is subsequently not entered into the study.

## 2.4 MULTIPLE COMPARISONS/MULTIPLICITY

The safety and tolerability of different dose levels of Ikt-148009 will be assessed as an overall evaluation of all safety endpoints. A formal statistical hypothesis of safety endpoints will not be tested. The efficacy endpoints will be tested in hierarchical order by endpoint within dose group. First, the change in MDS-UPDRS Parts II + III endpoint for the high dose will be compared to placebo. Next, if there is a statistically significant difference in the high dose levels for the MDS-UPDRS Parts II + III endpoint, the testing will continue by comparison of high dose vs placebo for the next endpoint in the hierarchy. The procedure will continue similarly for all remaining secondary endpoints. If all efficacy endpoints are significant for the high dose group, then testing will proceed for the middle dose group, then the low dose group.

In case not all endpoints are compared as a part of the hierarchical testing procedure, the statistical tests will be nominal and reported for descriptive purposes only and interpreted in an exploratory manner.

The order of hierarchical testing will be as follows:

1. MDS-UPDRS Parts II + III

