5.2 Multiplicity Adjustment

The safety and tolerability of different dose levels of IkT-148009 will be assessed as an overall evaluation of all safety endpoints. No formal statistical hypothesis will be tested.

The efficacy endpoints will be tested in hierarchical order by endpoint and within each endpoint by dose. First, the primary endpoint will be compared to placebo for the primary endpoint. If the difference for the high dose is statistically significant, the middle dose will be compared to placebo for the primary endpoint. If the difference in both high and middle doses are statistically significant, the low dose will be compared to placebo for the primary endpoint.

Next, if there is a statistically significant difference in all dose levels for the primary endpoint, the testing will continue by comparison of high dose vs placebo for the secondary endpoint ranked highest, followed by comparisons of the same endpoint for the middle and low dose, as long as all previous comparisons have been statistically significant. The procedure will continue similarly for all remaining secondary endpoints.

In case not all endpoints are compared as a part of the hierarchical testing procedure, the statistical tests will be reported for descriptive purposes and interpreted in an exploratory manner.

The steps in the hierarchical testing procedure are as follows:

1. MDS-UPDRS Parts II + III
2. Patient Global Impression-Severity (PGI-S)
3. Clinician Global Impression of Severity (CGI-S)
4. MDS-UPDRS Part II
5. MDS-UPDRS Part III
6. MDS-UPDRS Part I
7. Non-Motor Symptom Scale (NMSS)
8. Complete Spontaneous Bowel Movement score (CSBM)
9. ESS (Epworth Sleepiness Scale)
10. SE-ADL Scale

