## 1 INTRODUCTION

This study is being conducted for the clinical development of IKT-148009 (also known as Risvadotinib) for Parkinson's disease (PD). The purpose of this statistical analysis plan (SAP) is to describe the procedures and the statistical methods that will be used to analyze and report results based on Protocol IKT-148009-201 version 6.4, dated October 19, 2023.

The document may evolve over time to reflect protocol amendments, regulatory discussions, and other important changes. However, the SAP will be finalized, approved by the Sponsor, and placed on file before the database is locked and the study unblinded. In case of any differences between the SAP and the protocol, the SAP will be the final determinant. Deviations from the final approved plan will be noted in the clinical study report.

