Categorical endpoints (PGI-S, CGI-S) will be analyzed using the GLIMMIX procedure for binomial data with the logit link. The model will include the observed binomial values from all post-baseline visits as the response values and the treatment group, visit and the interaction between the treatment group and visit as fixed factors. The baseline value will be used as a covariate in the model. “Improved” is defined as at least a whole number decrease in score for PGI-S and CGI-S. Response values will be the proportion who improved since baseline at each post-baseline visit. The proportion who improved at each assessment will be presented, along with the odds ratio, 95% CI and  $p$ -value. Only the proportion who improved at Week 12 will be used for statistical comparison.

Endpoints will be tested in the order presented in [Section 2.4](#) with 2-sided  $\alpha=0.05$ . Endpoints not compared as part of the hierarchical testing procedure will be reported for descriptive purposes only.

Each of the secondary efficacy endpoints is described in [Section 3.2](#).

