## 6 SUMMARY OF MAJOR CHANGES IN THE PLANNED ANALYSES

The definition of mITT was changed to exclude those who were randomized prior to Protocol version 6.1. A Full Analysis Set (FAS) was defined to include everyone who meets the other requirements for inclusion in the mITT, including those randomized prior to Protocol version 6.1. The FAS will be used to perform a sensitivity analysis on the MDS-UPDRS Parts II+III.

The order of hierarchical testing for statistical significance was changed to test all endpoints in the highest dose first (200 mg), then the 100 mg dose, then the 50 mg dose. Testing order of the endpoints was changed.

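### Does SAP 2.4 let 50 mg be formally tested after 100 mg has failed, and so lose control of the familywise error at 5%?

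*SAP*

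**What the plan says.** SAP 2.4 orders the tests by endpoint within dose. It starts with MDS-UPDRS Parts II + III at 200 mg, moves on only after a significant result, and runs through 14 endpoints. One sentence then crosses the doses: "If all efficacy endpoints are significant for the high dose group, then testing will proceed for the middle dose group, then the low dose group".

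SAP 4.2.3 tests each endpoint at two-sided 0.05, points back to 2.4 for the order, and adds: "Endpoints not compared as part of the hierarchical testing procedure will be reported for descriptive purposes only". SAP 2.4 likewise calls such tests nominal. SAP 6 records that the testing order "was changed to test all endpoints in the highest dose first (200 mg), then the 100 mg dose, then the 50 mg dose", and that the endpoint order was changed too.

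Protocol 5.2 nested the tests the other way, dose within endpoint, and wrote out its conditions. For the first endpoint: "If the difference in both high and middle doses are statistically significant, the low dose will be compared to placebo for the primary endpoint". Later tests go ahead "as long as all previous comparisons have been statistically significant". SAP 1 settles conflicts between the two documents: "In case of any differences between the SAP and the protocol, the SAP will be the final determinant".

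**The concern.** The cross-dose sentence in SAP 2.4 contains one condition, success at 200 mg. It then lists the other two doses with nothing between them. Protocol 5.2 did have a condition for the low dose, but the SAP rearranged that procedure and takes precedence. On a strict reading, three rules might govern entry to 50 mg: all 14 endpoints significant at 100 mg, only the first endpoint significant at 100 mg, or no requirement at 100 mg.

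Only the first rule is a single fixed sequence of 3 × 14 = 42 tests. Suppose 200 mg passed everything and 100 mg missed an endpoint. The choice of rule would then decide whether a 50 mg p-value below 0.05 was a formal result or a nominal one. If that were settled after unblinding, it would be settled with the answer in view.

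**Working it through.** **Inputs.** From the SAP: 14 endpoints per dose (2.4); two-sided 0.05 per test (4.2.3); 1:1:1:1 target allocation with one placebo arm (1.3.1); 30 per group, difference 5, SD 6, 10% dropout (1.3.3). Correlations between endpoints are not given, so they are assumed and varied.

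**The plan's own figure.** 30 × 0.9 = 27 evaluable per arm. Standard error = 6 × √(2/27) = 1.633, and 5/1.633 = 3.062. Power = Φ(3.062 − 1.960) = 86.5% (85.2% with the t distribution). The stated power above 80% reproduces. The documents state no familywise error figure.

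**All 14 required at 100 mg.** No false positive can occur unless the first true null hypothesis in the sequence is rejected, which has probability at most 0.05. The familywise error is therefore at most 5.0%.

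**No requirement at 100 mg, both lower doses inactive, 200 mg certain to pass.** A false positive occurs when either dose is significant on Parts II + III, so the error is P(|Z₁| > 1.96 or |Z₂| > 1.96). With equal arms the two contrasts share the placebo mean, so their correlation is (σ²/n)/(2σ²/n) = 0.5. The result is 9.07%. The independent limit is 1 − 0.95² = 9.75%.

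**100 mg active on Parts II + III only, 50 mg inactive.** The two chances of error now fall on different endpoints, PDQ-39 at 100 mg and Parts II + III at 50 mg. Their correlation is 0.5 times the endpoint correlation. For endpoint correlations of 0.3, 0.5, 0.7 and 0.9 the error is 9.69%, 9.59%, 9.43% and 9.21%. This applies to the first-endpoint rule as well as to no rule.

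**Simulation of the full sequence**, 200,000 runs per case, 200 mg certain to pass, endpoint correlation 0 to 0.8:

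| Requirement at 100 mg | Both lower doses inactive | 100 mg active on first endpoint only |
|---|---|---|
| All 14 endpoints | 4.97–5.06% | 4.97–5.06% |
| First endpoint only | 4.97–5.06% | 9.30–9.82% |
| None | 9.01–9.09% | 9.30–9.82% |

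**The same with 200 mg uncertain.** Give 200 mg the planned standardised effect (3.062) on every endpoint and leave the lower doses inactive:

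| Endpoint correlation | 200 mg passes all 14 | Error, all 14 required | Error, no requirement |
|---|---|---|---|
| 0 | 13.0% | 0.57% | 1.03% |
| 0.3 | 33.0% | 1.68% | 3.02% |
| 0.6 | 51.4% | 2.48% | 4.52% |
| 0.8 | 64.3% | 2.86% | 5.26% |

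If 100 mg also has the planned effect on the first endpoint only, the error with no requirement is 1.01%, 3.11%, 4.55% and 5.06%. Under the first-endpoint rule it is 0.93%, 2.97%, 4.38% and 4.84%. With lower doses inactive, having no requirement exceeds 5% only once 200 mg has roughly a 60% chance of passing everything. An assumed 99% power on every endpoint with correlation 0.9 (96.8% chance of passing) gives 8.16%.

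**The text side by side.** SAP 6 describes a change in the order of doses and endpoints; it does not say that passing the earlier tests ceased to matter. The protocol's general condition, that every earlier comparison must have succeeded, can be applied to the new order without conflict and gives the all-14 rule. Nothing in SAP 2.4, 4.2.3 or 6 makes the first endpoint alone a gate between doses, so that rule has no basis in the text. SAP 2.4 also writes out the endpoint-to-endpoint step only for the high dose. Everyone would carry that step over to 100 mg because the procedure is hierarchical, and the same inference supplies the step from 100 mg to 50 mg.

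**The case for a change.** The strongest case for a change is that SAP 2.4 writes out the gate within 200 mg and the gate from 200 mg to 100 mg, and then stops. The protocol's gate was built for a different nesting, and the SAP overrides the protocol. The clause making tests outside the hierarchy nominal cannot decide the matter, because it presupposes knowing which tests are inside. One sentence would close the gap at almost no cost.

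The label can matter if every dose is active. With motor endpoints at 85% power, the others at 80% and correlation 0.5 (all assumed), a formal 50 mg result on Parts II + III arises in 17.3% of trials under the all-14 rule and 31.9% with no requirement. Over the assumed scenarios the gap between these two rules is 2 to 16 percentage points.

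What stands: the condition is not written down, and the limiting error rates are correct. What does not stand is that the rule is open. The SAP overrides the protocol where the two differ, and silence about a pass rule is not a stated difference. A 50 mg test that ignored the 100 mg results would not belong to a hierarchy in any ordinary sense.

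**Conclusion.** No change to the plan follows. This is an unwritten step that an analyst would fill with the all-14 rule, and under that rule the familywise error is at most 5.0%. The 9.1% to 9.7% range belongs to looser readings in a limiting case where 200 mg is practically certain to win on all 14 endpoints. At the planned effect on every endpoint the looser readings give about 1% to 5%. These figures rest on equal arms, a shared placebo and assumed endpoint correlations.

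The consequence is also narrow. There is no primary efficacy endpoint (SAP 1.2.2). Estimates, confidence intervals and p-values are the same under every reading, and the question arises only after 14 successes out of 14 at 200 mg. Writing the condition out would record what the section already implies. Allowing formal 50 mg tests after partial success at 100 mg, with alpha split to pay for it, would be a different design choice with its own loss of power, not the repair of an error.
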